8.3.2 Response Criteria for Overall Response

The primary endpoint of this VATCH sub-protocol is to determine whether the MEK inhibitor trametinib administered once a day on a continuous dosing schedule to subjects with Ras/MAPK pathway driven Vascular Anomalies provides an objective response at the end of cycle 6. Assessment of response is an individualized response criterion based on radiologic assessment, Patient Reported Outcome Measurements (composite score) and Clinical Benefit Assessment. Disease Response is determined by the local institution/investigator and is defined below.

Clinically meaningful response:

A clinically meaningful response includes a substantial response, Intermediate response or stable disease at the timing of protocol assessment.

Assessment of individualized response criteria after 6 cycles for primary endpoint and then every 6 months.

Substantial response:

- Improvement in Radiologic assessment (if applicable) by 20% AND
- Improvement in Global Health PROs by 3T-score points* AND
- Improvement in at least 1 CBA as reported by the clinician AND
- No clinically meaningful worsening in any measure

Intermediate response:

- Improvement in Radiologic assessment (if applicable) by 20% OR
- Improvement in Global Health PROs by 3 T-score points* OR
- Improvement in at least 1 CBA as reported by the clinicians AND
- No clinically meaningful worsening in any measure

Stable disease:

- No clinically meaningful improvement or worsening from screening in
 - Radiologic assessment (if applicable), OR
 - Global Health PROs*, OR
 - CBA as reported by the clinician

Worsening disease:

- Clinically meaningful worsening in
 - Radiologic assessment (if applicable) by 20%, OR
 - Global Health PROs by 3T-score points*, OR
 - CBA as reported by the clinician
 - **Regardless** of any concomitant improvement in other measures.

*Prior review articles have indicated that a change of 2 to 6 T-score points is the minimum important change (MIC) for PROMIS measures. PROMIS leadership recommends 3 T-score points as the MIC^{61,62}.

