Efficacy Evaluations	
1. Radiologic assessment (if applicable):
 
 - For subjects with radiologically evaluable disease only. Subjects without radiologically evaluable disease may have a CBA substituted for radiologic evaluation. -MRI evaluation will be at screening, and at the end of cycle 6, 12, and 24 (if applicable) on treatment. If there are signs of worsening, earlier assessment should be done. 
2. Patient reported outcome (PRO) measurements:
 
 - Screening to end of study- Every 6 cycles 
3. Clinical Benefit Assessment (CBA):
 
 - Screening to the end of study- every 6 cycles
Safety Evaluations	
Safety assessments will be conducted through the study (according to the assessment schedule)
 
 • Monitoring of adverse events (AEs) and serious adverse events (SAEs) • Physical examination • Body weight and vital signs • Height and body mass index (BMI) • Karnofsky/Lansky performance status • Laboratory assessment including hematology, biochemistry, urinalysis, and coagulation. • Serum or urine pregnancy test for subjects of child-bearing potential • Echocardiography

- Ophthalmologic exams

Statistical and Analytic Plan

For all the analyses, subjects who received any dose of trametinib will be included in the analyses. For the primary efficacy endpoint of objective response at the end of cycle 6, we will test a null hypothesis of response of 40% against an alternative hypothesis of response rate of 65%. We will follow the Simon's optimal two-stage design: an interim analysis will be conducted after 16 subjects have been observed for response, and if 6 or fewer intermediate, substantial, or stable responses are observed, the trial will be stopped for futility; otherwise, the trial will continue to enroll a total of 39 subjects and at the end of the trial if 20 or more responses are observed, the treatment will be declared promising. This design provides $\geq 90\%$ power when the true response rate is 65% and yields a one-sided type I error of ≤ 0.05 when the true response rate is 40%.

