8.3.3 Duration of Response

Duration of Overall Response: The overall response (substantial or intermediate) duration is measured from the time of primary endpoint measurement (6 cycles) until the first date that recurrent or progressive disease is objectively documented (taking as reference for progressive disease the smallest measurements recorded since the treatment started).

Duration of Stable Disease: Stable disease is measured from the start of the treatment until the worsening disease criteria are met, or patient on evaluation has a substantial or intermediate response.

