9.1 Sample Size and Power

For the primary efficacy analysis of objective response at the end of cycle 6, we will test a null hypothesis of response of 40% against an alternative hypothesis of response rate of 65%. We will follow the Simon's optimal two-stage design: an interim analysis will be conducted after 16 subjects have been observed for response, and if 6 or fewer response is observed, the trial will be stopped for futility; otherwise the trial will continue to enroll a total of 39 evaluable subjects and at the end of the trial if 20 or more responses are observed, the treatment will be declared promising. This design provides $\geq 90\%$ power when the true response rate is 65% and yields a one-sided type I error of ≤ 0.05 when the true response rate is 40%.

For evaluating of toxicity, a sample size of 39 provides 86% probability to observe at least one toxicity event when the underlying true toxicity rate is 5%, so that we have good confidence to observe a rare toxicity type. In addition, this sample size provides a reasonable precision on the estimate of the toxicity rate. For example, with 7 observed toxicity events

out of 39 subjects, the estimated toxicity rate is 18%, with the 95% exact confidence interval (CI) as 8% - 34%.

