9.3 Statistical Analyses Plan

For all the analyses, subjects who received any dose of trametinib will be included in the analyses. The primary efficacy endpoint is objective response (including both response and partial response) at the end of cycle 6 and the primary safety endpoint is toxicity of trametinib. We will use binomial distributions to estimate the response and the toxicity rates with their 95% exact CIs. For the second primary efficacy endpoint of responses at the end of cycles 12 and 24, the response rate will also be calculated with 95% CI. For the secondary endpoint of duration of response, time from initial response to disease progression will be examined, and subjects will be censored at the last adequate disease assessment if no progression occurred by that time. We will use the log-rank tests and/or Cox proportional hazard regression to analyze the endpoint. Should the data suggest the violation of the

proportional hazard assumption, we will consider an alternative method such as accelerated failure time model analysis.

Secondary data analyses will be performed for the secondary outcomes of longitudinal measurements of radiologic assessment, PROMIS Patient Reported Outcome measurements, and Clinical Benefit Assessments, taken at screening, and at the end of cycles 6, 12, 18, and 24. The longitudinal data will be analyzed separately at each follow-up time point and together longitudinally. The paired t-test will be used to look at changes in these measures from pre-treatment levels to the post-treatment level (follow-up at cycle 3) to evaluate the treatment's short-term effects. Mixed effects models will be used for longitudinal analysis to evaluate changes in these measures over time. Should the data suggest the distributions of the measurements deviate from normal distributions, we will consider nonparametric alternatives such as Wilcoxon signed rank test or transformation. Relationships between PROMIS measures and other variables such as pain will be investigated using correlation analysis. Lastly, exploratory analyses will be performed for biomarker measures such as cell-free DNA. Descriptive statistics will be generated to summarize data.

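### The event counted in the primary test is not defined consistently: stable disease counts in the synopsis futility rule and in 8.3.2, but not in 8.3.3 or 9.3

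*Protocol*

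**What the plan says.** The protocol describes the counted event in five places.

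- **Synopsis, Statistical and Analytic Plan.** The trial stops for futility "if 6 or fewer intermediate, substantial, or stable responses are observed" among the first 16 subjects. The success clause, 20 or more of 39, refers only to responses.
- **Section 8.3.2.** The primary endpoint is introduced as objective response at the end of cycle 6. The section then adds: "A clinically meaningful response includes a substantial response, Intermediate response or stable disease at the timing of protocol assessment". Stable disease is defined there as no meaningful improvement or worsening from screening.
- **Section 8.3.3.** "The overall response (substantial or intermediate) duration is measured from the time of primary endpoint measurement (6 cycles"). Stable disease has a separate duration, which ends on worsening or on a substantial or intermediate response.
- **Section 9.1.** The null rate is 40% and the alternative 65%. The rule reads "an interim analysis will be conducted after 16 subjects have been observed for response, and if 6 or fewer response is observed", and then "at the end of the trial if 20 or more responses are observed, the treatment will be declared promising". No categories are named.
- **Section 9.3.** The primary efficacy endpoint is "objective response (including both response and partial response) at the end of cycle 6".

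The primary objective (synopsis and section 3.2) is the proportion of subjects whose response is both objective and beneficial.

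**The concern.** The go/no-go decision rests on a count out of 16 and then out of 39, and the protocol does not settle which subjects are counted. A subject with no change at cycle 6 is a success under the synopsis futility rule. Under 9.3, read with 8.3.3, the same subject appears to be a failure. The same data could therefore lead to opposite decisions.

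Two consequences follow.

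- If stable disease counts throughout, the trial tests whether more than 40% of subjects avoid worsening over 24 weeks. Without a control group, a positive result may not separate benefit from stability.
- If stable disease counts at the interim only, the two stages use different endpoints. The error rates in 9.1 assume one endpoint at both.

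**Working it through.** **Inputs.** Sections 9.1 and synopsis: n1 = 16, stop at 6 or fewer; n = 39, promising at 20 or more; null 0.40, alternative 0.65. The untreated rates of non-worsening and of chance improvement are not in the protocol, so they are assumed and varied.

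**Formula.** For a true rate p of the counted event,

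P(promising) = Σ over x = 7 to 16 of Bin(x; 16, p) × P[Bin(23, p) ≥ 20 − x].

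**The plan's own figures first.** At p = 0.65 the formula gives 0.958, so the stated power of at least 90% is met. At p = 0.40 it gives 0.093, not the stated 0.05 or less. That discrepancy is a separate matter. The exact Simon optimal design for these inputs has the same sizes but stops at 7 or fewer of 16 and requires 21 of 39 (type I error 0.046, power 0.901). Both rules are shown below so that the two issues are not confused.

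**Case A: stable disease counts at both stages.** The counted event is then non-worsening. For an inert drug, p is the untreated non-worsening rate:

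| Assumed non-worsening | Printed rule (6/16, 20/39) | 7/16, 21/39 |
|---|---|---|
| 30% | 0.004 | 0.001 |
| 40% | 0.093 | 0.046 |
| 50% | 0.467 | 0.323 |
| 60% | 0.870 | 0.763 |
| 70% | 0.990 | 0.968 |

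Correcting the cut-offs does not remove the dependence on the assumed rate.

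The assumed rate is itself sensitive to how easily a measure worsens by chance. Suppose the three measures are independent and each worsens with probability w, so that non-worsening is (1 − w)³:

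- w = 0.10 gives 0.73, and P(promising) = 0.996 under the printed rule.
- w = 0.20 gives 0.51, and 0.525.
- w = 0.30 gives 0.34, and 0.019.

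**Case B: only substantial or intermediate response counts.** With 15% improving by chance (assumed), P(promising) is below 0.001. With 30% it is 0.004.

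**Case C: stable disease counts at the interim only.** Suppose 40% improve (the null rate) and a further 20% are stable (assumed).

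- *Interim.* The count has rate 0.40 + 0.20 = 0.60. The stopping probability P[Bin(16, p) ≤ 6] falls from 0.527 at p = 0.40 to 0.058 at p = 0.60.
- *Final.* The count has rate 0.40. Summing over the three-category outcome of the first 16 subjects gives P(promising) = 0.102, against 0.093 with one definition. This is close to the single-stage value P[Bin(39, 0.40) ≥ 20] = 0.102.

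In this case the futility stop is largely lost, while the false-positive rate changes little.

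**The case against.** Several points on the other side are sound.

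- **The definitions are not all of the same thing.** Section 8.3.3 concerns duration, a secondary endpoint. Section 8.3.2 never states that objective response equals clinically meaningful response. The synopsis names stable disease only in its futility clause. A reader might infer three flatly incompatible definitions of the primary endpoint; the text supports less. The direct conflict is between the synopsis (and arguably 8.3.2) and 9.3. Section 8.3.3 is supporting evidence.
- **No untreated rate is given.** A reader might infer that an inert drug would pass, because malformations are often stable untreated. The protocol does not support this. It enrols symptomatic subjects in need of medical therapy, describes a fluctuating course, and calls a subject worse on any one of three measures, including a 3-point PRO change. Non-worsening could be uncommon, and at 30% an inert drug almost never passes.
- **Counting stable disease may be intended.** Two places name it, and preventing worsening can be a legitimate aim. That would be a defensible endpoint if it were stated throughout and if 40% and 65% were set for it.
- **The category wording is a smaller matter.** The unbracketed AND in Intermediate looks ambiguous, but the Worsening definition already overrides any improvement. The ORs in Stable are most naturally read as denying change in all three measures.

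None of this says which subjects are counted. An unseen analysis plan cannot cure it either, because the protocol's own statements disagree.

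**Conclusion.** The point holds as an inconsistency in the definition of the primary event, and it should be resolved before the interim. No assumption is needed for that part, which can be read from the text.

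The size of the consequence depends on a rate the protocol does not give. With stable disease counted, the chance that an inert drug is called promising under the printed rule runs from 0.004 to 0.99 as assumed non-worsening goes from 30% to 70%, passing about one half near 50%. With stable disease excluded, it is below 0.001 at 15% chance improvement. A false positive is therefore a real possibility, not a certainty. It would also go too far to say that a positive result would carry no information about benefit. It may fail to distinguish benefit from stability.

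**What to change.** Before the 16-subject interim, use one definition at both stages, in the synopsis and in 8.3.2, 9.1 and 9.3.

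- **Preferred.** Count substantial or intermediate response at the end of cycle 6, which matches the primary objective. Remove stable disease from the synopsis futility rule, and name the two categories in 9.1 and in both synopsis clauses. Replace the undefined labels in 9.3. In 8.3.2, rename the group that includes stable disease as disease control and report it descriptively. Confirm that 40% and 65% were set for this definition.
- **Alternative.** If stable disease is meant to count, say so in every one of these places and justify 40% and 65% from an untreated non-worsening rate.
- **Tidy-up, in 8.3.2 and the Abstract, which repeats the criteria.** Join the Stable items with AND so that categories cannot overlap. Bracket Intermediate as (radiologic or PRO or CBA improvement) and no worsening in any measure.

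**Cost.** The edits are wording, but the preferred choice lowers the observed response rate, and the hypothesised rates must be rechecked. For example, if the 65% had included 20 points of stable disease (assumed), the rate under the preferred definition would be 65% − 20% = 45%. The probability of success under the printed rule would then be 0.243 instead of 0.958, and the sample size would need reconsidering.

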8.3.3 Duration of Response

Duration of Overall Response: The overall response (substantial or intermediate) duration is measured from the time of primary endpoint measurement (6 cycles) until the first date that recurrent or progressive disease is objectively documented (taking as reference for progressive disease the smallest measurements recorded since the treatment started).

Duration of Stable Disease: Stable disease is measured from the start of the treatment until the worsening disease criteria are met, or patient on evaluation has a substantial or intermediate response.

9 STATISTICAL CONSIDERATIONS

This is a Phase II non-randomized study to evaluate trametinib in children and young adults with Ras/MAPK Driven Vascular Anomalies. The primary efficacy endpoint is objective response at the end of cycle 6 and the primary safety endpoint is toxicity of trametinib. Secondary endpoints duration of response, response at scheduled protocol visits during the extension period, and assessment of changes in symptoms and complications over time. Biomarker analysis is exploratory in this protocol.

9.1 Sample Size and Power

For the primary efficacy analysis of objective response at the end of cycle 6, we will test a null hypothesis of response of 40% against an alternative hypothesis of response rate of 65%. We will follow the Simon's optimal two-stage design: an interim analysis will be conducted after 16 subjects have been observed for response, and if 6 or fewer response is observed, the trial will be stopped for futility; otherwise the trial will continue to enroll a total of 39 evaluable subjects and at the end of the trial if 20 or more responses are observed, the treatment will be declared promising. This design provides $\geq 90\%$ power when the true response rate is 65% and yields a one-sided type I error of ≤ 0.05 when the true response rate is 40%.

For evaluating of toxicity, a sample size of 39 provides 86% probability to observe at least one toxicity event when the underlying true toxicity rate is 5%, so that we have good confidence to observe a rare toxicity type. In addition, this sample size provides a reasonable precision on the estimate of the toxicity rate. For example, with 7 observed toxicity events

out of 39 subjects, the estimated toxicity rate is 18%, with the 95% exact confidence interval (CI) as 8% - 34%.

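### The written two-stage boundaries (stop at 6 or fewer of 16, promising at 20 or more of 39) have a one-sided type I error of 9.3%, not the stated 5% or less

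*Protocol*

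**What the plan says.** Section 9.1 (Sample Size and Power) gives every element of the rule.

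- Hypotheses: "we will test a null hypothesis of response of 40% against an alternative hypothesis of response rate of 65" (per cent).
- Design: "We will follow the Simon's optimal two-stage design".
- Interim: a single look at 16 subjects, where "if 6 or fewer response is observed, the trial will be stopped for futility".
- Continuation: "otherwise the trial will continue to enroll a total of 39 evaluable subjects".
- Final decision: "at the end of the trial if 20 or more responses are observed, the treatment will be declared promising".

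It then states that power is at least 90% at a true rate of 65% and that the one-sided type I error is at most 0.05 at a true rate of 40%.

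The Statistical and Analytic Plan entry of the synopsis repeats the sizes, both cut-offs and both operating characteristics. Its futility sentence reads "if 6 or fewer intermediate, substantial, or stable responses are observed, the trial will be stopped for futility". The same cut-offs therefore stand in two places.

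**The concern.** A two-stage rule is fully determined by its two sample sizes and two cut-offs, so its type I error and power can be calculated exactly and compared with what the protocol claims. Twenty of 39 is 51.3%, and under a 40% null the expected count is 39 × 0.40 = 15.6. A cut-off that close to the null expectation looks too lenient for a 5% test.

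This is the trial's primary efficacy decision rule: it governs both the futility stop and whether trametinib is called promising. If the type I error is well above 5%, a drug with the protocol's own uninteresting response rate passes more often than the sponsor, the DSMB and the IRB have been told. If the futility cut-off is also too low, more children and young adults are enrolled on such a drug before the trial ends.

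**Working it through.** **Inputs**, all from Section 9.1: null rate 0.40; alternative rate 0.65; stage 1 n₁ = 16, continuing if X₁ ≥ 7; total n = 39, so stage 2 has 39 − 16 = 23 subjects; success if the total is 20 or more. The calculation does not depend on which categories count as a response.

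**Formula.** With true rate p,

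P(declared promising) = Σ over x = 7,…,16 of P(Bin(16, p) = x) × P(Bin(23, p) ≥ 20 − x).

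**Type I error of the written rule (p = 0.40)**

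| x in stage 1 | P(X₁ = x) | needed in stage 2 | P(at least that many of 23) | product |
|---|---|---|---|---|
| 7 | 0.1889 | 13 | 0.0813 | 0.0154 |
| 8 | 0.1417 | 12 | 0.1636 | 0.0232 |
| 9 | 0.0840 | 11 | 0.2871 | 0.0241 |
| 10 | 0.0392 | 10 | 0.4438 | 0.0174 |
| 11 | 0.0142 | 9 | 0.6116 | 0.0087 |
| 12 | 0.0040 | 8 | 0.7627 | 0.0030 |
| 13 to 16 | 0.0009 | 7 to 4 | 0.876 to 0.995 | 0.0008 |
| **Total** | | | | **0.0926** |

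The stated figure is at most 0.05, and 0.0926 / 0.05 = 1.85. A simulation of 2 million trials gave 0.0925.

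**Power of the written rule (p = 0.65).** The same sum gives 0.9575. The power statement is reproduced; the type I error statement is not.

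**Early stopping under the null.** P(Bin(16, 0.40) ≤ 6) = 0.527, so the expected sample size is 16 + 23 × (1 − 0.527) = 26.9.

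**Other readings and single corrections**

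| Stop at | Promising at | Type I error | Power |
|---|---|---|---|
| ≤ 6 of 16 | ≥ 20 of 39 (as written) | 0.0926 | 0.9575 |
| ≤ 6 of 16 | ≥ 21 of 39 | 0.0526 | 0.9340 |
| ≤ 6 of 16 | ≥ 22 of 39 | 0.0270 | 0.8921 |
| ≤ 7 of 16 | ≥ 20 of 39 | 0.0772 | 0.9196 |
| ≤ 7 of 16 | ≥ 21 of 39 | 0.0460 | 0.9012 |
| no interim | ≥ 20 of 39 | 0.1021 | 0.9732 |

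With the interim cut-off at 6 of 16, no final cut-off at 39 meets both stated properties: 21 misses on type I error and 22 misses on power.

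**The design that is named.** An exhaustive search over both sample sizes and both cut-offs (total up to 45) looked for the smallest expected sample size at 40%, subject to type I error ≤ 0.05 and power ≥ 0.90. It returns n₁ = 16, n = 39, stop at 7 or fewer, promising at 21 or more. Type I error is 0.0460 and power 0.9012. Early stopping under the null is 0.716 and the expected sample size is 16 + 23 × (1 − 0.716) = 22.5.

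The sample sizes match the protocol exactly, and both cut-offs differ by one. The usual notation for this design is 7/16 and 20/39, with the drug rejected at or below each number. Turning a reject-at-or-below-20 bound into an accept-at-20 bound would produce the written final rule.

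**The case against.** The fairest defence concerns emphasis. This is a single-arm, open-label Phase II trial whose positive outcome is called promising. Safety is also a primary endpoint and has its own pausing rule in Section 9.2. The power statement is correct for the rule as written. The two cut-offs do not contribute equally: moving only the final one to 21 brings the error to 0.0526, which rounds to 0.05, so the interim cut-off accounts for little of the excess. The protocol also states no early-stopping probability or expected sample size, so 52.7% and 26.9 contradict no figure in it.

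These points stand, and they limit how the finding should be described: an error in the primary efficacy decision rule, due mostly to the final cut-off. They do not remove it. The protocol's limit is at most 0.05, and 0.0526 exceeds it. The interim cut-off must also change if the rule is to be the optimal design that the protocol names. The weak futility look is a consequence of missing that design, not a second error.

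A separate SAP would not cure this, because the protocol itself states both the rule and the property that the rule lacks.

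**Conclusion.** The concern holds. As written in Section 9.1 and the synopsis, the rule has a one-sided type I error of 9.26% at a 40% response rate. That is about 1 chance in 11 of calling an uninteresting drug promising, where the protocol states at most 1 in 20. Power is 95.8%, so that claim is met. The rule is not Simon's optimal design for these inputs; both cut-offs are one response too low. As a result, a drug at the null rate passes the interim look 47.3% of the time, against 28.4% under the named design.

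A final count of exactly 20 of 39 is where the two rules give opposite conclusions: the written rule would declare success, and the named design would not.

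The result rests only on the protocol's own inputs, on independent subjects with a common response rate, and on exactly 16 and 39 subjects entering the two decisions. Section 4.7.2 expects about 45 enrolled to obtain 39 evaluable, and Section 9.3 analyses everyone dosed. The figures here, including those for the corrected rule, apply to a denominator of 39.

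**What to change.** In Section 9.1 and in the synopsis, change both cut-offs. Suggested text: If 7 or fewer responses are observed among the first 16 subjects, the trial will stop for futility; otherwise enrolment will continue to 39 evaluable subjects, and the treatment will be declared promising if 21 or more responses are observed.

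Both the futility sentence and the success sentence must be changed in each place. The sample sizes and the stated type I error and power stay as they are, and both statements are then true (4.60% and 90.1%).

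The cost is a short protocol amendment and no extra subjects. The final bar rises by one response and power falls from 95.8% to 90.1%, still within the stated target. The change is simple only before the interim look, and the protocol does not say whether that look has taken place. If 16 subjects have already been assessed, moving the futility boundary is no longer a neutral edit. The amendment should then say what was known when it was made and report the type I error of the rule actually followed.
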